3. PK samples will be collected before study medication administration on these days if the visit date coincides with a day of injection; therefore study medication should be administered on site in that case. If the visit does not correspond to an injection day, the PK sample will be taken at anytime during the visit. Exact date and time of sampling should be recorded. See [Section 5.4](#)
4. Oral glucocorticoids have to be started on day 4 (or day 1 if IV steroids were already received) and tapered to 10mg prednisone equivalent within 12 weeks.
5. Starting from week 2, patients have to administer the injections with BI 655064/placebo by themselves always 7 days after the previous dose.
6. Safety lab tests : details of tests is given in [section 5.3.3](#)
7. Pregnancy test will be performed in women of childbearing potential every 4 weeks. A serum pregnancy test will be performed at screening visit. Urine dipstick tests will be done during the screening phase (8-10 days after the first test) and immediately before starting medication. It will be repeated at visits every 4 weeks and will be provided for at home pregnancy testing as soon as visit intervals are > 4 weeks,. In case of a positive urine pregnancy test result, a blood sample for serum pregnancy test will be drawn for confirmation. Only those females with a negative pregnancy test will receive study medication and will be allowed to start treatment with MMF
8. Will be measured in serum and urine
9. Questionnaires should be completed in the following order: LupusPRO, SF-36, FACIT-F, before any other visit assessment
10. EOT visit has to be carried-out for all patients when they stop treatment. At week 52, patients who reach at least partial response (based on values obtained at week 46) will be offered to enter a maintenance trial (trial 1293.13). Patients who stopped treatment before week 52 will not be allowed to participate in the maintenance trial.
11. Follow up visits to be performed after end of treatment except for patients entering the maintenance trial 1293.13 and patients who have withdrawn drug prematurely
12. For randomized patients leaving the study before the planned EOS, their vital status should be collected at week 60

TABLE OF CONTENTS

TITLE PAGE	1
CLINICAL TRIAL PROTOCOL SYNOPSIS	2
FLOW CHART	5
TABLE OF CONTENTS	9
ABBREVIATIONS	12
1. INTRODUCTION.....	15
1.1 MEDICAL BACKGROUND	15
1.2 DRUG PROFILE	16
2. RATIONALE, OBJECTIVES, AND BENEFIT - RISK ASSESSMENT	18

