HRQoL	Health related Quality of Life
HV	Healthy Volunteer
i.v.	intravenous
IB	Investigator's Brochure
IC	Inhibitory concentration
ICH	International Conference of Harmonisation
IEC	Independent Ethics Committee
IRB	Institutional Review Board
IRT	Interactive Response Technology
ISF	Investigator Site File
ITP	Immune thrombocytopenia
ITT	Intention to Treat
LupusPRO	Lupus patient-reported outcome
LN	Lupus Nephritis
MCP1	Monocyte Chemoattractant Protein-1
MCPmod	Multiple Comparison Procedure with modelling
MedDRA	Medical Dictionary for Drug Regulatory Activities
MMF	Mycophenolate
MRD	Multiple Rising Dose
MRR	Major Renal Response
MTX	Methotrexate
NOAEL	No Observed Adverse Effect Level
p.o.	per os (oral)
PD	Pharmacodynamics
PK	Pharmacokinetics
PRR	Partial renal Response
q1w	once a week
RA	Rheumatoid Arthritis
RBC	Red Blood Cell
RCTCAE	Rheumatology Common Terminology Criteria for Adverse Events
REP	Residual effect period, after the last dose of medication with measureable drug levels or pharmacodynamic effects still likely to be present
RNA	Ribonucleic Acid
RO	Receptor Occupancy
s.c.	subcutaneous
SAE	Serious Adverse Event
SLE	Systemic Lupus Erythematosus
SOC	Standard of Care
SOP	Standard Operating Procedure
SmPC	Summary of Product Characteristics
SRD	Single Rising Dose

SUSAR	Suspected Unexpected Serious Adverse Reaction
TB	Tuberculosis
TCM	Trial Clinical Monitor
TMF	Trial Master File
TSAP	Trial Statistical Analysis Plan
ULN	Upper Limit of Normal
WBC	White Blood cell

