4.2.2 Restrictions

4.2.2.1 Restrictions regarding concomitant treatment

Concomitant medications (or therapy) to provide adequate care may be given as clinically necessary. If a restricted concomitant therapy is necessary, treatment with study medication should be permanently discontinued

The [Table 4.2.2.1: 1](#) specifies periods before randomization and for the whole duration of the study including the Follow-up, when specific drugs are allowed or restricted.

Table 4.2.2.1: 1 Permitted and Restricted medications

Therapy	Prior to Study	Screening Period	Randomized Treatment Period		Follow up Period
			SOC Initial phase week 0-26	SOC week 26-52	
Azathioprine	Permitted on maintenance therapy	Permitted on maintenance therapy	Not permitted	Permitted if MMF not tolerated or not authorised	Permitted
Cyclophosphamide	Not permitted (6 m prior to randomisation)	Not permitted	Not permitted	Not permitted	Not Permitted
MMF	Permitted if dose ≤ 2 g/day; doses ≤ 3 g/day permitted within 6 weeks prior randomisation	Permitted within 6 weeks prior randomisation	Permitted max 3g/day	Permitted Max 2g/day	Permitted
Cyclosporine - Tacrolimus	Not permitted 4 weeks before randomisation	Not permitted	Not permitted	Not permitted	Permitted if needed based on inv decision
Treatment with any biologic B-cell depleting therapy (e.g. anti-CD20,antiCD22) or abatacept*	Not permitted (12 m prior to visit 2)	Not permitted	Not permitted	Not permitted	Not permitted
Belimumab, antiBLyS	Not Permitted (3 months or 5 half-lives whichever is longer when used for non renal SLE, 12 months when used for renal SLE)	Not permitted	Not permitted	Not permitted	Not permitted
Investigational Medication	Not permitted (6m or 5 half-lives prior to visit 2)	Not permitted	Not permitted	Not permitted	Not permitted
IV glucocorticoids	Allow 3 g IV total max within 6 weeks prior randomisation; a single pulse should not be >1000 mg		Permitted as part of the trial regimen, according to the protocol	Not permitted	Permitted

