5.3.6 Adverse event collection and reporting

AE Collection

The following must be collected and documented on the appropriate eCRF by the Investigator:

- From signing the informed consent onwards through the Residual Effect period (REP), until trial completion, all AEs (serious and non-serious), and all AESIs.

[figure not shown]

Figure 5.3.6:1 AE collection

The REP is defined as 50 days after the last trial medication application. All AEs which occurred through the treatment phase and throughout the REP will be considered as on treatment please see [section 7.3.4](#). Events which occurred after the REP will be considered as post treatment events.

After the last per protocol contact the Investigator does not need to actively monitor patients for AEs. However, if the Investigator becomes aware of SAEs or AESIs that occurred after the last per protocol contact, the SAEs and AESIs should be reported by the Investigator to the Sponsor if considered relevant by the Investigator.

AE reporting to sponsor and timelines

The Investigator must report SAEs, AESIs, and non-serious AEs which are relevant for the reported SAE or AESI, on the BI SAE form via fax immediately (within 24 hours) to the Sponsor's unique entry point (country specific contact details will be provided in the ISF). In specific occasions the Investigator could inform the Sponsor upfront via telephone. This does not replace the requirement to complete and fax the BI SAE form.

For Japan: All SAEs and AESIs must be reported immediately to the head of the trial site. With receipt of any further information to these events, a follow-up SAE form has to be

provided. For follow-up information the same rules and timeline apply as for initial information.

Information required

For each AE, the Investigator should provide the information requested on the appropriate (e)CRF pages and the BI SAE form, e.g. onset, end date, intensity, treatment required, outcome, seriousness, and action taken with the investigational drug(s). The Investigator should determine the causal relationship to the trial medication, and any possible interactions between the investigational drug and a Non-Investigational Medicinal Product.

The following should also be recorded as an (S)AE in the (e)CRF and SAE form (if applicable):

- Worsening of the underlying disease or of other pre-existing conditions

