6.2.3 Follow Up Period and Trial Completion

6.2.3.1 End of Treatment (EOT) Visit:

All patients will be asked to return for the EOT visit within 7 days from the last dose of study medication (either at week 52 for completers, or when a patient prematurely discontinues the drug). For details description of the trial procedures at EOT, refer to the [Flow Chart](#). 2 times 24h collection of urine has to be organized for this visit.

For patients that are eligible to participate in the extension trial 1293.13, the EOT visit will occur on the same day as the Visit 1 of the roll-over trial.

6.2.3.2 Follow-Up (FU) and End of Study (EOS) Visit:

After the end of treatment visit, patients who completed the 52 weeks treatment but are not eligible for the extension trial will return for a follow-up visit (after 4 weeks) and an EOS visit, 8 weeks after EOT.

Patients who are eligible for the extension trial will not have to complete the FU visit nor the EOS visit, but only the trial completion page will have to be completed.

During FU and EOS visits, the investigator will continue to follow-up on AEs that are not yet recovered. At EOS visit, the investigator needs to confirm whether the AEs are sufficiently followed up and provide documentation in the patient's medical records and on the eCRF.

For details description of the trial procedures at FU and EOS visits, refer to the [Flow Chart](#).

6.2.3.3 Continuation of the study for patients who withdrew drug prematurely (before completion of the 52 weeks treatment):

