In case a patient has to discontinue the trial drug, prior to having completed the 52 weeks treatment (i.e., prior to visit 16), he will be invited to attend a subset of visits as originally planned until and including visit 16: visit 5 (week 4), visit 8 (week 12), visit 11 (week 26), visit 14 (week 40) and an end of study visit at 52 weeks. During these visits, the patient should undergo selected examinations: physical examination, AE and CT collection, serum creatinine and spot urine test to assess the renal function. Other safety laboratory tests, PK sample, ADA, soluble protein biomarkers and anti-ds-DNA and complement will be collected at all visits until up to 12 weeks after End of Treatment. If the next FUP visit is planned more than 12 weeks after EOT, please have all optional tests performed at least once in the FUP period: i.e. if the patient EOT is V11 (W26), the next visit will be V14 (week 40): optional tests must be done at week 40, even if the time between week 26 & 40 is >12 weeks.

The visits may continue even though the patient will be allowed to participate in another investigational study after his withdrawal (discontinuation plus 28 days). The need for visits in case of premature drug withdrawal will be explained to the patients. In case the patient discontinued more than 8 weeks before week 52, no further follow up would be needed after week 52. In case the patient discontinued less than 8 weeks before week 52, the last follow-up visit will be 8 weeks +/- 5 days after discontinuation. In case the patient does not show-up at these visits, vital status information will be sought at planned EOS visit.

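### Early stoppers may enter another investigational study at 28 days, inside the protocol's own 50-day residual effect period and against its restricted-medication table (minor)

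*Protocol*

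**What the plan says.** - **Entry rule.** Protocol 6.2.3.3 invites patients who stop drug before week 52 to a reduced set of visits. It adds that these may continue even though "the patient will be allowed to participate in another investigational study after his withdrawal (discontinuation plus 28 days".
- **Residual effect period.** The protocol's abbreviation list defines REP as "Residual effect period, after the last dose of medication with measureable drug levels or pharmacodynamic effects still likely to be present". Section 5.3.6 gives its length: "The REP is defined as 50 days after the last trial medication application". Sections 5.3.6 and 7.3.4 count adverse events in that period as on treatment.
- **Restricted medication.** Section 4.2.2.1 says that Table 4.2.2.1:1 applies "for the whole duration of the study including the Follow-up, when specific drugs are allowed or restricted". The investigational medication row begins "Not permitted (6m or 5 half-lives prior to visit 2" and is negative in every later column: screening, weeks 0-26, weeks 26-52 and follow-up.
- **SAP safety analysis.** Sections 6.1, 7.8.1 and 7.8.2 assign adverse events and laboratory values to the treatment period up to last dose plus 50 days.
- **SAP deviations.** Table 6.2:1, code D1, lists investigational medication through week 52 as an important protocol deviation. It makes no exception for patients already off drug under 6.2.3.3.

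**The concern.** Two rules in the same protocol give different answers. The table bars investigational medication throughout, while 6.2.3.3 permits entry to an investigational study at day 28. A site following one breaks the other, and SAP D1 takes the table's side.

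The 28-day figure also sits inside the window in which the protocol itself regards BI 655064 levels or effects as still likely. A second investigational agent started then would share that window, and any event or laboratory change would be tabulated under the randomised arm. Safety and tolerability are stated objectives (2.2), and dose choice rests on efficacy and safety together (7.1). It is therefore worth keeping the on-treatment window free of a second unapproved product where this is cheap to do.

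**Working it through.** The plan gives no figure to reproduce here, so the check is a timeline in days.

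**Inputs.** Entry at discontinuation + 28 days (6.2.3.3). REP of 50 days from last dose (5.3.6). End-of-treatment (EOT) visit within 7 days of last dose (6.2.3.1). Week 52 visit on day 365 ± 3 and end of study on day 421 (Flow Chart). Last dose at week 51 (Table 4.1.4:1). Minimum of 46 weeks' treatment for the per-protocol set (SAP 6.3), and for using week 52 laboratory data in early stoppers (SAP 6.6.1). Week w falls on day 1 + 7w.

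**1. Overlap ceiling.** 6.2.3.3 does not say whether discontinuation means the last dose or the EOT visit.
- From last dose: 50 − 28 = 22 days.
- From an EOT visit on day 7: 50 − (7 + 28) = 15 days.

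**2. Joining is not dosing.** Two assumptions about the other study show the range.
- Screening of 7-28 days, as in this trial: first dose on day 35-56, overlap 15 to 0 days. On the EOT reading: day 42-63, overlap 8 to 0 days.
- A washout of 6 months or 5 half-lives, whichever is greater, as in this trial's exclusion criterion 7: overlap 0.

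**3. Reach of D1.** D1 runs to week 52. A stop at week 48 (day 337) permits entry on 337 + 28 = day 365, the nominal week 52 visit. Stops after about week 48 fall outside D1. Patients treated for less than 46 weeks are already outside the per-protocol set and are non-responders in the ITT analysis. D1 can therefore change per-protocol membership only for stops at about weeks 46-48.

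**4. Effect of day 51.**
- REP overlap: 0 days.
- Extra wait: 51 − 28 = 23 days, or 51 − 35 = 16 days if the present rule runs from a day-7 EOT visit.
- Latest stop allowing entry by the week 52 visit: 365 − 51 = day 314, and (314 − 1)/7 = week 44.7. With the +3-day window it is day 317, or week 45.1. Both precede week 46 (day 323), so no patient treated for at least 46 weeks could be on another product at that visit.

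**The case against.** **Perhaps 6.2.3.3 is simply the specific rule for early stoppers.** The stated consequence of needing a restricted drug is "If a restricted concomitant therapy is necessary, treatment with study medication should be permanently discontinued", which has no force for someone already off drug. Flow Chart footnote 11 requires follow-up visits "except for patients entering the maintenance trial 1293.13 and patients who have withdrawn drug prematurely". This is a sensible way to reconcile the texts, but neither document states it. The weeks 26-52 column is also a calendar period through which early stoppers are still seen. The contradiction should be settled in writing.

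**Perhaps 28 days has a pharmacological basis.** Sections 1.2 and 4.1.3 are blank in the public copy, so this cannot be excluded. The point rests only on the mismatch with the protocol's own REP.

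**Attribution is already handled case by case.** Protocol 5.3.5.1 has the investigator weigh confounders such as concomitant medication. Concomitant therapy is still collected at the retained visits, and SAP 7.2 lists it by patient. This stands: a case can be traced, and no distortion of event rates is shown.

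**D1 is not automatic.** A reader might infer that D1 will log every permitted entry and remove the patient. The documents do not support that. Its entries are manual, the list is a working one, and exclusion from the per-protocol set is left to the review meetings.

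**The rule might look uniquely short, or unfair to completers.** Not every post-dose clock reaches day 50: the blood-donation limit after MMF is 6 weeks (4.2.2.2). Completers not entering trial 1293.13 have follow-up "and an EOS visit, 8 weeks after EOT", about 421 − 358 = 63 days after a week 51 dose. However, early stoppers may have left for a flare or an adverse event and cannot enter 1293.13, so earlier access for them is defensible. Neither comparison is needed here.

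**Rescue therapy also falls inside the REP.** True, and the flag proposed below does not cover it. Rescue follows treatment guidelines and raises no conflict between protocol sections, so it is a separate matter.

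**Conclusion.** The point holds as a minor one. As worded, 6.2.3.3 contradicts Table 4.2.2.1:1, and its 28-day wait ends inside the 50-day REP. Possible overlap with another investigational agent is at most 22 days, or 15 on the EOT reading. It may be zero, depending on the other study's screening or washout, which the documents do not give. The number of patients who would join is also not given and is probably small.

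A reader might go further and infer biased safety rates or a compromised primary endpoint. The documents support neither. Stoppers before week 46 are non-responders whatever they take afterwards. SAP 6.6.1 rule 2 makes a non-responder of any early stopper who then used prohibited medication known to affect complete renal response. What remains is a narrow band of stops at about weeks 46-48 in which another product could be in use by week 52.

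**What to change.** 1. **Protocol 6.2.3.3:** replace the 28-day wait with entry from day 51 after the last dose, that is, after the REP. Naming the last dose also removes the ambiguity about the starting point.
2. **Table 4.2.2.1:1:** add a note giving off-drug early stoppers the matching exception.
3. **SAP D1:** word it so that entry allowed by the protocol version in force is not a deviation, including entry at days 28-50 under the present rule. Week 52 data collected while on another investigational product should still be reviewed for the per-protocol set.
4. **Listings:** keep the 50-day window as the main safety analysis. In the existing adverse event and laboratory listings, flag values after the first dose of another investigational product. No second set of summary tables is needed.

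**Cost.** A few patients wait about 23 days longer, with guideline rescue therapy available meanwhile (3.3.4.1). The protocol changes need an amendment approved by ethics committees and authorities in about 22 countries, so they are best bundled with other changes. The SAP side is one line in D1 and one listing flag.

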7. STATISTICAL METHODS AND DETERMINATION OF SAMPLE SIZE

7.1 STATISTICAL DESIGN - MODEL

This trial is a study of proof of concept in patients with lupus nephritis. It is designed as a randomized, double-blind and placebo-controlled trial with 4 parallel groups (3 active vs. placebo).

The primary objective of this trial is to define one or more suitable doses regarding efficacy and safety for further pivotal testing in Phase III. For this purpose a multiple comparison procedure with modelling (MCPmod) approach is considered ([R10-1424](#), [R15-1961](#)).

7.2 NULL AND ALTERNATIVE HYPOTHESES

The primary endpoint is proportion of patients with complete renal response at week 52. The null hypothesis is that there is a flat dose response curve looking at the proportion of patients with complete renal response at week 52 in the placebo and the three BI 655064 dosage groups. The alternative hypothesis is that there is a non-flat dose response curve. Additionally it will be investigated whether at least one dose shows a modelled absolute benefit compared to placebo of at least 10%.

The MCPMod procedure allows for the simultaneous evaluation of different potential dose response patterns, whilst protecting the overall probability of type I error of 20%. The pre-specified models and their parameters used for this test are outlined in [Section 7.3.1](#) and [Section 7.7](#).

This is an exploratory trial and no formal statistical testing will be performed. Any p-values or confidence intervals provided are to be interpreted in an exploratory sense.

7.3 PLANNED ANALYSES

All the analyses will be performed in an exploratory fashion to better-understand the efficacy and safety profile of the drug under study in the selected patient population. The primary analysis will follow the intention to treat principle (ITT), thus it is based on the FAS (Full Analysis Set) and analysis will be performed as randomised. The FAS contains all treated patients who have a valid baseline value and at least one valid value in at least one primary or secondary efficacy endpoint on treatment.

Safety analysis will be based on all treated patients and the safety profile will be compared in a descriptive manner between the three experimental arms and the control arm.

All individual data will be listed. Adherence to the protocol (e.g. inclusion/exclusion criteria, times of measurement, completeness and consistency of data etc.) will be checked using the data recorded. Important protocol violations will be described in the TSAP. Standard statistical parameters (number of non-missing values, mean, standard deviation (SD), median, quartiles, minimum and maximum) or frequency tables will be calculated where

appropriate. In general, these parameters or frequencies will be calculated separately for each treatment group.

Data from subjects who are screened but not randomised will be listed but not included in any summary statistics.

7.3.1 Primary endpoint analyses

The primary endpoint is the proportion of patients with complete renal response after 52 weeks of treatment. Patients withdrawn due to non-response are considered non-responders for the analyses at 52 weeks.

The analyses for PoC and dose-finding will be performed using MCPMod techniques ([R10-1424](#), [R15-1961](#)) for binary data whereby several possible dose response models (patterns) will be evaluated (while keeping full control of the type I error) to identify the best-fitting model or subset of models. Due to the rareness of the disease and in order to have a feasible resulting sample size the global α -level has been chosen to be 20% one-sided.

A non-flat dose-response relationship is established if the null hypothesis of no dose effect (i.e. a flat dose response curve) is rejected for at least one of the pre-specified models with respect to the global alpha chosen.

For the sample size calculation, the maximum effect size is assumed to be 45% with the placebo effect size assumed to be 25%. Further details are given in [Section 7.7](#).

The following models shapes have been selected as the candidate set of possible dose response patterns:

Emax : $E_0 + E_{max} * d / (ED_{50} + d)$

Exponential : $E_0 + E_1 * (\exp(d/\delta) - 1)$

Quadratic : $E_0 + \beta_1 * d + \beta_2 * d^2$

Sigmoid Emax : $E_0 + E_{max} * d^h / (ED_{50}^h + d^h)$ Model shapes are illustrated in figure [7-3-1: 1](#). Note that the actual shapes are applied on the parameter scale (logit for binary data) according to Pinheiro et al. ([R15-4293](#)).

[figure not shown]

Figure 7.3.1 : 1: Shape of the models within the candidate set

If a non-flat dose response relationship is established, the significant model(s) from the above candidate set are refitted to the data without any parameter assumptions to generate new estimates of the model parameters from the data. The final model will be obtained via model averaging across the significant models based on Akaike Information Criterion (AIC). The target dose(s) can then be determined from that model by any incorporating information on the minimum clinically relevant effect as well as safety information. The target dose to be chosen should show a benefit of at least 10% in complete renal response rate at week 52 compared to the placebo. This will be measured on the modelled efficacy and only doses within the dose range investigated (0mg-240mg) will be considered although the actual modelling will be performed on a broader range of doses including extrapolation.

If considered necessary and for the purpose of further model refinement, MCPMod might be repeated on the primary endpoint but with an extended set of shapes including the original candidates. Additionally to that covariates may be taken into account in a sensitivity analysis. Finally the approach described by Klingenberg et al ([R15-0407](#)) will be taken into account to show robustness of the primary analysis. Details of these analyses will be described in the TSAP.

Comparisons between treatment groups will be exploratory in nature and based on the numerical comparison of the respective response rates. In addition, unadjusted absolute risk differences of the complete renal response at week 52 between the BI 655064 arms and the placebo group will be analysed. The proportion of responders in each arm, the risk difference

between each arm and placebo and 95% exact confidence intervals will be displayed. Finally, a logistic regression model on the proportion of patients with complete renal response at week 52 with factors treatment and race as strata will be applied. More details on the above analyses as well as additional sensitivity analyses will be given in the TSAP.

